### 11.1.2 Documenting and Reporting Adverse Events

The Investigator is responsible for routine assessments of AEs throughout the course of the study. All clinical complaints, symptoms, or signs that meet the AE definition will be documented in the patient’s record and entered in the study database. Source documentation

should be maintained that allows for clear identification of each AE and the following parameters:

- Date of onset
- Date of resolution (or indication that the event continues as of the final visit)
- Intensity (mild, moderate, severe)
- Seriousness (per SAE definition)
- Relationship to study treatment
- Outcome

For study data collection purposes, the outcome of AEs captured in the database will be reviewed and made final at the time of the final study evaluation for each patient. If the AE is ongoing, this will be reflected in the record. However, the study Investigator is responsible for following all AEs until resolution or until no longer of clinical concern.

#### **11.1.2.1 Assessment of Intensity (or Severity)**

The intensity of each AE will be assessed using the following categories: mild, moderate, and severe.

- **Mild:** Easily tolerated by the patient, causes minimal discomfort and does not interfere with everyday activities.
- **Moderate:** Sufficiently discomforting to interfere with normal everyday activities; intervention may be needed.
- **Severe:** Prevents normal everyday activities; treatment or other intervention usually needed.

There is an important distinction between a severe AE and a serious AE. The term “severe” designates the intensity of the event, while a “serious” AE meets specific criteria promulgated in 21 CFR 312.32 and described in Section [11.1.1](#).

#### **11.1.2.2 Assessment of Relationship to Study Treatment**

The relationship of an AE to the administration of the study drug is to be assessed according to the following definitions:

No (unrelated, not related, unlikely to be related) – The time course between the administration of study drug and the occurrence or worsening of the AE rules out a causal relationship and another cause (concomitant drugs, therapies, complications, etc) is suspected.

Yes (possibly, probably, or definitely related) – The time course between the administration of study drug and the occurrence or worsening of the AE is consistent with a causal

relationship and no other cause (concomitant drugs, therapies, complications, etc) can be identified.

The definition implies a reasonable possibility of a causal relationship between the event and the study drug. This means that there are facts (evidence) or arguments to suggest a causal relationship.

The following factors should also be considered:

- The temporal sequence from study drug administration-
  - The event should occur after the study drug is given. The length of time from study drug exposure to event should be evaluated in the clinical context of the event.
- Underlying, concomitant, intercurrent disease-
  - Each report should be evaluated in the context of the natural history and course of the disease being treated and any other disease the patient may have.
- Concomitant drug-
  - The other drugs the patient is taking or the treatment the patient receives should be examined to determine whether any of them might be recognized to cause the event in question.
- Known response pattern for this class of study drug-
  - Clinical and/or preclinical data may indicate whether a particular response is likely to be a class effect.
- Exposure to physical and/or mental stresses-
  - The exposure to stress might induce adverse changes in the recipient and provide a logical and better explanation for the event.
- The pharmacology and pharmacokinetics of the study drug-
  - The known pharmacologic properties (absorption, distribution, metabolism, and excretion) of the study drug should be considered.

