Suspected Adverse Reaction	
An AE for which there is a reasonable possibility that the investigational product caused the AE. A “reasonable possibility” means there is evidence to suggest the investigational product is causally related to the AE. Examples include:
 
A single occurrence of an event that is uncommon and known to be strongly associated with an active ingredient or other component regardless of formulation;
 
One or more occurrences of an event that is not commonly associated with an active ingredient or other component, but is atypical in the study population;
 
The observation, when looking at data summaries, that a condition expected for the study population is occurring with increased frequency in comparison to concurrent or historical controls.

Treatment-Emergent AE (TEAE)	An AE that occurs after the patient has received the investigational product. AEs that occur during the Screening and Washout periods prior to treatment with the investigational product are not TEAEs.
Unexpected AE or Unexpected Suspected Adverse Reaction	Any AE or suspected adverse reaction not listed in the current Investigator’s Brochure (IB) or for which the specificity or severity of the event is not consistent with the IB; or, if an IB is not required or available, the specificity or severity of which is not consistent with the risk information described in the general investigational plan or elsewhere in the current application, as amended. For example, under this definition, hepatic necrosis would be unexpected (by virtue of greater severity) if the IB only referred to elevated hepatic enzymes or hepatitis.

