### **11.3 Expedited Reporting**

The Sponsor will report all relevant information about SUSARs that are fatal or life-threatening as soon as possible to the FDA and in any case no later than 7 days after knowledge by the Sponsor/designee of such a case, and the relevant follow-up information will subsequently be communicated within an additional 8 days.

All other SUSARs will be reported to the FDA as soon as possible but within a maximum of 15 days of first knowledge by the Sponsor/designee.

The Sponsor/designee will also inform all Investigators as required.

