No deaths occurred in healthy volunteers who received ricolinostat. Among the 229 individuals with refractory multiple myeloma treated with ricolinostat, 11 (5%) deaths occurred, of which 1 was in the monotherapy study and 10 were in the combination studies. No clear dose relationship to ricolinostat was observed, and all deaths occurred in patients who were ill with advanced

multiple myeloma. The causes of death were attributed to several different events: cardiac arrest/sudden death (N=2), pulmonary embolism (N=2), sepsis/septic shock (N=3), pneumonia (N=2), bacterial meningitis (N=1), and ‘mental status changes,’ with a number of terminal events described in the narrative (N=1). None of these deaths was judged by the assessing Investigator as likely due to treatment with ricolinostat, and all were consistent with the severe and progressive underlying neoplastic disease (refractory multiple myeloma) of the patients being studied. Further details are available in the Investigator’s Brochure.

In the one healthy volunteer study conducted to date, the most common adverse effect reported in a study of healthy volunteers administered ricolinostat doses of 120 and 160 mg in crossover fashion was throat irritation (3 patients), and no SAEs were reported.

As described above, the overall body of safety data does not predict serious safety concerns specific to ricolinostat. However, as a result of their underlying disorder, patients with diabetes are at increased risk for a number of medical problems such as renal impairment and increased risk for infections. The available data do not suggest that ricolinostat is likely to increase these risks, but it is important to monitor these issues, and therefore the protocol will include specific monitoring for several potential AEs and laboratory changes designated as events of special interest and described in Section 11.10.2.2 below. Finally, with respect to skin biopsy, although patients with diabetes are at increased risk for poor wound healing related to vascular disease, the skin biopsy for IENFD is superficial, small, and commonly performed in patients with diabetic neuropathy, and poses minimal safety risk.

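### The yes/no causality definitions are not complementary: an event with fitting timing and an identified other cause has no category, contrary to the protocol's own reasonable-possibility standard.

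*Protocol*

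**What the plan says.** Protocol section 11.1.2.2 presents two definitions as the basis on which relationship is to be assessed.

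- **Yes.** The category opens with the words "Yes (possibly, probably, or definitely related", so one definition serves all three grades. It asks for timing consistent with a causal "relationship and no other cause (concomitant drugs, therapies, complications, etc) can be identified".
- **No.** This category also takes in unlikely to be related. It asks for timing that "rules out a causal relationship and another cause (concomitant drugs, therapies, complications, etc) is suspected".

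The same section then adds: "The definition implies a reasonable possibility of a causal relationship between the event and the study drug". It goes on to list factors to consider: temporal sequence, underlying disease, concomitant drugs, class response pattern, physical or mental stress, and pharmacology.

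Protocol section 11.1.1 defines a suspected adverse reaction as "An AE for which there is a reasonable possibility that the investigational product caused the AE". SAP section 4.4.1 uses the same standard. Neither asks that other causes be absent.

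The relatedness call is used in three places:

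- Treatment-related events are tabulated under Protocol section 10.3.7 and SAP section 11.1. Neither section says how the category is defined.
- Under Protocol section 11.1.3, serious events beyond 30 days after the final dose must be reported only if the investigator considers them related.
- Protocol section 11.3 sets the timelines for suspected unexpected serious reactions: 7 days if fatal or life-threatening, otherwise 15.

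**The concern.** A two-way classification should place every event in exactly one category. Here each definition joins a timing condition and an other-cause condition with *and*, so events that meet one condition but not the other may belong nowhere. The label and the condition also pull apart. Possibly related ordinarily describes an event for which another explanation exists, yet here it carries the requirement that none can be identified. Likewise, unlikely carries the requirement that timing rules causation out.

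The missing case is a plausible one in this trial. Every patient has diabetes, and Protocol section 11.9 says that "patients with diabetes are at increased risk for a number of medical problems such as renal impairment and increased risk for infections". Protocol section 8.4.2 lets patients continue one medication for painful neuropathy. Active treatment is daily for about 24 weeks (Protocol section 8.2.1), so timing will seldom exclude study drug for an on-treatment event.

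Section 11.9 also attributes earlier episodes of neutropenia, anemia and renal change to underlying disease and concurrent chemotherapy, and section 11.10.2.2 names anemia, neutropenia and renal impairment as events of special interest. A *Yes* rule that excludes any event with an identified alternative explanation is poorly suited to testing that attribution.

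At stake are the consistency of the treatment-related tables and the reporting of late serious events.

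**Working it through.** No rate, power or sample size is involved and the plan gives no figure to reproduce. The check sets the two definitions against the possible combinations of their own conditions.

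The thresholds for another cause differ. *No* needs one to be suspected; *Yes* is blocked only when one can be identified. So other cause has three levels: none, suspected but not identified, and identified. Crossing these with two timing levels gives 2 × 3 = 6 combinations.

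| Timing | Other cause | Meets *Yes*? | Meets *No*? | Category |
|---|---|---|---|---|
| Consistent | None | Yes | No | *Yes* |
| Consistent | Suspected, not identified | Yes | No | *Yes* |
| Consistent | Identified | No | No | **None** |
| Rules out | None | No | No | **None** |
| Rules out | Suspected, not identified | No | Yes | *No* |
| Rules out | Identified | No | Yes | *No* |

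Two of the six combinations have no category. (If suspected and identified are merged, the grid is 2 × 2 and two of four are empty.) The two gaps do not matter equally:

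1. **Timing rules out causation, no other cause.** This has no practical weight. No reader would call such an event related.
2. **Timing consistent, other cause identified.** This is the real gap. The event fails *Yes* on the other-cause condition and fails *No* on the timing condition.

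Now apply the reasonable-possibility standard to the second gap. An identified alternative cause does not by itself remove a reasonable possibility that study drug caused or worsened the event. Under section 11.1.1, and under the explanatory sentence in section 11.1.2.2, such an event can be a suspected reaction. Under the *Yes* definition it cannot be related in any grade. One of the examples in section 11.1.1 makes the contrast plain: a condition expected in the study population counts if it occurs more often than in controls, and such a condition has a background explanation by its nature.

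The listed factors do not decide the case. They say what to weigh, not which category to use when timing fits and another cause has been identified.

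**The case against.** The strongest reply is that section 11.1.2.2 already contains the right standard. Its explanatory sentence speaks of a reasonable possibility, and the text adds that facts or arguments suggesting causation suffice. A sensible investigator could follow that and code a mixed-cause event *Yes*. This stands as a limit: the defect is an inconsistency within the section, not the absence of the right standard. But the sentence is offered as what the definition implies, and the definition does not imply it, so a site that follows the definition literally reaches a different answer.

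Stronger readings are tempting and should be resisted:

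- **That related events would necessarily be under-called.** The mixed-cause event is barred from *No* as firmly as from *Yes*. The text establishes ambiguity; under-calling is a risk, not a fixed direction.
- **That this is the commonest kind of event.** Section 11.9 speaks only of increased risk. That all patients have diabetes does not make diabetes the identified cause of any particular event, and any percentage would be invented.
- **That the field decides which events go to the regulator.** Section 11.1.1 defines a suspected reaction without reference to this yes/no field, and section 11.3 places expedited reporting on the sponsor. All serious events from first dose to 30 days after the last must be reported within 24 hours whatever their causality (section 11.1.3). What remains is influence: the documents describe no separate sponsor causality assessment.

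Other safeguards also stand. Adverse and serious events are summarized by arm regardless of relatedness. Hematology and eGFR changes have numerical triggers (sections 11.10.2.2 and 11.10.2.2.1). The monitoring committee sees unblinded safety data (section 11.10.1.2). Planned follow-up ends about 4 weeks after the last dose and the half-life is about 3 hours (section 5.4), so few late serious events may turn on the call. These limit the harm; none corrects individual relatedness calls or the tables built on them.

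**Conclusion.** The point holds as a defect of wording. The two definitions are not complementary, and they conflict with the reasonable-possibility standard in the same section and in Protocol section 11.1.1. An event with consistent timing and an identified alternative cause has no category and, read literally, cannot be even possibly related.

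The wording gap is certain; its effect is not quantifiable from the documents. The expected consequences are inconsistent coding or under-calling in the treatment-related tables, and possible non-reporting of some serious events after the 30-day window. An influence on expedited-report assessment is possible but not shown. The practical weight assumes that at least some sites apply the definitions as written and that mixed-cause events occur in useful number. Both are plausible here and neither is measured. The change should be made, but the trial's main between-arm safety comparison does not depend on it.

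**What to change.** Reconcile section 11.1.2.2 with section 11.1.1 by making the categories complementary:

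- *Yes*: there is a reasonable possibility that study drug caused or worsened the event, whether or not another possible cause exists.
- *No*: there is no reasonable possibility that it did.

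Keep the listed factors as considerations rather than conditions. The adverse event and serious adverse event forms are not among the documents; if they repeat the current definitions, align their text.

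The cost is one paragraph in an amendment, a site memo and, if needed, form help text. The downside is that somewhat more events will be coded as related in both arms, with some extra expedited-report assessments. Events already coded under the current wording should be identifiable, so that a change in the related count is not mistaken for a change in safety.

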### **11.1.3 Special Procedures for Reporting Serious Adverse Events**

SAEs require additional detailed reports and follow-up. An SAE must be reported to the Sponsor immediately (within 24 hours) so as to facilitate discussion and implementation of necessary follow-up measures, and to enable the Sponsor to submit necessary reports to regulatory authorities, other Investigators, and IRBs. The Sponsor may request additional data and follow-up SAE reports to facilitate full disclosure to regulatory authorities, other Investigators, and IRBs in accordance with relevant regulation.

#### **Initial Reports**

All SAEs occurring from the time of first dose (start of Pain Observation period) of study drug until 30 days following the final dose of study drug must be reported to Medpace Clinical Safety

within 24 hours of the knowledge of the occurrence. After the 30-day reporting window, any SAE that the Investigator considers related to study drug must be reported to Medpace Clinical Safety or the Sponsor/designee.

To report the SAE, complete the SAE form electronically in the EDC system for the study. When the form is completed, Medpace Safety personnel will be notified electronically by the EDC system and will retrieve the form. If the event meets serious criteria and it is not possible to access the EDC system, send an e-mail to Medpace Safety at [[contact]](mailto:[contact]) or call the Medpace SAE reporting line (phone number listed below), and fax/e-mail the completed paper SAE form to Medpace (fax number listed below) within 24 hours of awareness. When the EDC system becomes available, the SAE information must be entered within 24 hours of the system becoming available.

Safety Contact Information: Medpace Clinical Safety

Medpace SAE reporting line – USA:

[contact], dial 3 or [contact], dial 3

[contact] or [contact]

E-mail: [[contact]](mailto:[contact])

Follow-Up Reports

The Investigator must continue to follow the patient until the SAE has subsided or until the condition becomes chronic in nature, stabilizes (in the case of persistent impairment), or the patient dies.

Within 24 hours of receipt of follow-up information, the Investigator must update the SAE form electronically in the EDC system for the study and submit any supporting documentation (eg, patient discharge summary or autopsy reports) to Medpace Clinical Safety via fax or e-mail. If it is not possible to access the EDC system, refer to the procedures outlined above for initial reporting of SAEs.

## **11.2      Pregnancy Reporting**

If a patient becomes pregnant during the study or within the safety Follow-up period defined in the protocol, the Investigator is to stop dosing with study drug immediately and the patient should be withdrawn from the study. Early termination procedures should be implemented at that time.

A pregnancy is not considered to be an AE or SAE; however, it must be reported to Medpace Clinical Safety within 24 hours of knowledge of the event. Medpace Clinical Safety will then provide the Investigator/site the Exposure In Utero (EIU) form for completion. The Investigator/site must complete the EIU form and fax or e-mail it back to Medpace Clinical Safety.

If the female partner of a male patient becomes pregnant while the patient is receiving study drug or within the safety Follow-up period defined in the protocol, the Investigator should notify Medpace Clinical Safety as described above.

The pregnancy should be followed until the outcome of the pregnancy, whenever possible. Once the outcome of the pregnancy is known, the EIU form should be completed and faxed/e-mailed to Medpace Clinical Safety. If the outcome of the pregnancy meets the criteria for immediate

classification as an SAE (ie, postpartum complication, spontaneous abortion, stillbirth, neonatal death, or congenital anomaly), the Investigator should follow the procedures for reporting an SAE.

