During the 12-week randomized, double-blind, placebo-controlled Treatment period, patients will return for assessments as per the schedule of assessments shown in [Table 1](#). An electronic daily diary will be completed by patients to record study and rescue medication (acetaminophen) use, as well as NRS pain assessments. Rescue medication (as needed) and one permitted medication that has been used at a stable dose for at least 3 months prior to starting the Pain Observation period may be used during the study. Other pain medications are prohibited during the Treatment period. Diary data will be reviewed with the patient at each study visit to determine if further instruction is required and to document any discrepancies with study drug or rescue medication dosing.

At the conclusion of the approximately 12-week double-blind, placebo-controlled Treatment period, patients will enter an approximately 12-week open label Safety Extension period during which all patients will receive ricolinostat 120 mg daily and complete evaluations and clinic visits as per the schedule of events. At the conclusion of the Safety Extension, there will be an approximately 4-week washout and Safety Follow-up period, which will incorporate 2 visits at approximately 2 and 4 weeks following the final Safety Extension visit, with assessments performed as outlined in the schedule of assessments ([Table 1](#)).

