#### **7.3.1 Inclusion Criteria**

Eligible patients will meet the following criteria:

1. Able to understand the study's purpose and requirements, and able to voluntarily provide informed consent to participate.
2. Age  $\geq$  18 years and  $<$  80 years at the time of signing the ICF.
3. FOCBP must agree to use reliable contraceptive methods for the duration of the study and for at least 3 months after completing treatment with study drug. For the purposes of this study, reliable methods of contraception include abstinence, oral contraceptives, hormonal contraceptive implants such as Nexplanon, hormonal vaginal ring such as NuvaRing, intrauterine devices in place for at least 3 months, or barrier methods used in conjunction with spermicide. To be considered post-menopausal and of non-child-bearing potential, women less than 60 years with less than 2 years since their last period must have FSH  $>$  40 IU/L and estradiol  $<$  20 pg/mL unless on hormone replacement.

Male patients participating in the study must also agree to use these reliable contraceptive methods if sexually active with a FOCBP partner and also agree to abstain from sperm donation from Day 1 through 3 months after completing treatment with study drug.

4. Type 1 or Type 2 diabetes of at least 6 months duration that meets American Diabetes Association criteria (American Diabetes Association, 2020) with an HbA1c > 6.5% at the time of Screening. If the HbA1c at the time of Screening is less than 6.5%, evidence that the patient meets American Diabetes Association criteria for diabetes must be documented and reviewed with the Sponsor prior to entering the patient in the study. Additionally, the diabetes should be adequately controlled, with an HbA1c < 11% and no evidence of severe hypoglycemia requiring hospitalization within the past 6 months, and in the Investigator's judgment sufficiently stable to allow participation in the study.

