#### **11.10.2 Patient Level Risk Mitigation**

##### **11.10.2.1 Patient Exclusion**

Given the potential for undue risk, certain patients will be excluded from study participation as follows:

- Patients at risk for QT interval prolongation as a result of personal or family history, or with measured QTc prolongation on Screening ECG.
- Patients with any hematologic or select serum chemistry abnormalities suggesting serious, ongoing medical problems, including significant renal or hepatic impairment.
- Patients with significant comorbidities or other medical conditions, laboratory abnormalities, or psychiatric illnesses that would place the patient at increased risk.

- As the effect of ricolinostat on fetal development is not known, pregnant women or women wishing to become pregnant will be excluded from the study, as will FOCBP who do not agree to use contraception as outlined above. Breastfeeding mothers will also be excluded.

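### Pregnancy reporting in Protocol 11.2 runs only to the roughly 4-week safety follow-up (expressly for partners, by the natural reading for patients), although contraception is required for at least 3 months after treatment

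*Protocol*

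**What the plan says.** **Contraception period.** Inclusion criterion 3 (Protocol 7.3.1, repeated in the Synopsis and in SAP Exhibit 1) requires women of childbearing potential to use contraception "for the duration of the study and for at least 3 months after completing treatment with study drug". Men with a partner of childbearing potential must use the same methods and must also "abstain from sperm donation from Day 1 through 3 months after completing treatment with study drug". Section 11.10.2.1 gives the reason for the pregnancy and contraception restrictions: "As the effect of ricolinostat on fetal development is not known".

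**Pregnancy handling.** Section 11.2 has three relevant sentences.
- The first covers a patient who "becomes pregnant during the study or within the safety Follow-up period defined in the protocol". Its instruction is to stop study drug and withdraw the patient.
- The second says that a pregnancy is not itself an AE or SAE but must go to the safety group within 24 hours of the site knowing of it. That report leads to the exposure-in-utero form. The sentence has no end date of its own.
- The third covers the female partner of a male patient. Notification is required if she becomes pregnant "while the patient is receiving study drug or within the safety Follow-up period defined in the protocol".

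**Length of follow-up.** Section 7.1 says that after the Safety Extension "there will be an approximately 4-week washout and Safety Follow-up period". Section 9.7 places its two visits about 2 and 4 weeks after the last dose (Weeks 26 and 28). Section 9.7.2 treats the patient as having completed the study after the Week 28 visit, which is also the last scheduled pregnancy test.

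**The concern.** The protocol sets a precautionary period after the last dose and then appears to stop collecting pregnancies well before that period ends. A partner's conception six weeks after the last dose would fall inside the contraception requirement but outside the notification rule. For a female patient the same event has no clearly stated reporting duty.

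What is at stake is safety information. The pregnancy report and the exposure-in-utero form are the protocol's designated route for learning about a risk that it calls unknown. If only serious outcomes judged related arrive late by another route, normal outcomes are not systematically collected and there is no denominator for the abnormal ones.

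**Working it through.** **Inputs**
- Contraception after treatment: at least 3 months (Protocol 7.3.1), taken as 90 to 92 days, or about 13 weeks (91 days). This is a minimum.
- Safety follow-up: about 4 weeks (Protocol 7.1).
- Visit windows (Protocol Table 1): Week 24 is Day 166 to 170, Week 28 is Day 194 to 198. Nominal days (SAP Exhibit 4): 168 and 196.
- SAE reporting: all SAEs to 30 days after the final dose, and after that only those the investigator considers related (Protocol 11.1.3).

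**Step 1. Reproduce the plan's follow-up length.** 196 − 168 = 28 days = 4 weeks, as stated. The visit windows allow from 194 − 170 = 24 days to 198 − 166 = 32 days.

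**Step 2. Check that the study does not run longer for the patient.** Section 7.5 gives participation of up to about 34 weeks including follow-up. From Day −45 to Day 196, (45 + 196)/7 = 34.4 weeks. The study period therefore ends at Week 28 as well, and referring to the study adds nothing after it.

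**Step 3. The gap** = contraception period after the last dose − safety follow-up.

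| 3 months taken as | Follow-up | Gap (days) | Gap (weeks) |
|---|---|---|---|
| 91 days | 28 days | 63 | 9.0 |
| 90 days | 32 days | 58 | 8.3 |
| 92 days | 24 days | 68 | 9.7 |

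The central figure is 9 of 13 post-treatment weeks, 63/91 = 69% of that part. Ending the window at the 30-day SAE limit instead would hardly change it: (90 − 30)/7 = 8.6 to (92 − 30)/7 = 8.9 weeks.

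**Step 4. Put the gap in proportion.** Criterion 3 also covers time in the study. Counting from Day 1, the contraception period is about 24 + 13 = 37 weeks, and 9/37 = 24% lies outside the window. All time on treatment is inside it.

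**Step 5. Look for another rule that closes the gap.**
- AE collection ends at the follow-up visit or earlier discontinuation (11.1.1), and a pregnancy is not an AE or SAE (11.2).
- After 30 days the SAE rule takes related events only. Section 11.2 lists outcomes that qualify as SAEs, such as spontaneous abortion, stillbirth and congenital anomaly. One of these could enter late without an earlier pregnancy report, but only if the site hears of it and judges it related.
- No section of the protocol or SAP extends pregnancy reporting to 3 months.

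**Step 6. Early leavers.** Section 9.8 asks for the Week 24 final assessments and sets no follow-up length, so the end of their reporting window is not defined.

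**The case against.** **The patient sentence is not the reporting rule.** The phrase about the follow-up period introduces stopping drug and withdrawal, while the 24-hour reporting sentence is open-ended. This stands in part: only the partner sentence bounds notification expressly. For patients, dosing has already ended by follow-up, so the window can hardly be there only to trigger stopping drug. It reads most naturally as bounding the whole procedure, reporting included. Even on the open-ended reading, the patient and partner rules differ without explanation.

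**The gap is smaller than 69% suggests.** This stands. That share is of the post-treatment part only, and on-treatment time is fully covered.

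**Late pregnancies need not be lost.** A reader might infer that pregnancies in these weeks go unreported. The documents do not support that: voluntary reports are not barred and related SAEs remain reportable. What is missing is a clear duty.

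**Exposure by then may be negligible.** Section 5.4 gives a half-life of about 3 hours, so 28 days is 28 × 24/3 = 224 half-lives. The documents do not show that a conception at week 6 is an in-utero exposure, and they do not explain the choice of 3 months. This limits the importance of the point but does not remove the mismatch between two rules in the same protocol.

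**Early leavers.** A reader might infer that their window is shorter still. Section 9.8 is silent on its length, so the most that can be said is that it is undefined.

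**Instructions may exist elsewhere.** Consent pages were not available for review and may tell patients to notify the site after the study. No claim is made that such instructions are missing.

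**Conclusion.** The point holds as a mismatch between Section 11.2 and inclusion criterion 3. It is explicit for partners of male patients and is the most natural reading for female patients. About 9 of the 13 weeks after the last dose (range 8.3 to 9.7) carry no clear pregnancy-reporting duty.

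This rests on reading 3 months as 90 to 92 days and on the safety follow-up meaning the only period so defined, ending at Week 28. The documents give no expected number of pregnancies. I assume it is small, and the conclusion does not depend on it. No efficacy endpoint or analysis is affected. It is a worthwhile, inexpensive correction to safety reporting, and it makes no judgement on whether 3 months is the right contraception period.

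**What to change.** Reconcile Section 11.2 with criterion 3 in the reporting sentences only. In the 24-hour sentence for patients and in the partner-notification sentence, state that pregnancies are reportable through the end of the protocol's own contraception period after the last dose, including for patients who stop early.

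Leave the first sentence of 11.2 unchanged. Putting the longer period there would extend a stop-dosing and withdrawal instruction to patients who have already finished both drug and study.

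With this change the post-treatment gap goes from about 9 weeks to 0 (coverage from 4 of 13 weeks to 13 of 13). The cost is a wording change to two sentences at the next amendment. Reporting stays passive, with no added visit, test or analysis. The downside is occasional pregnancy follow-up after a patient's last visit.
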